6 DISCONTINUATION

6.1 Discontinuation of Individual Subject(s)

A discontinuation is a subject who enrolled in the study and for whom study treatment is permanently discontinued prematurely for any reason.

The subject is free to withdraw from the study treatment and/or study for any reason and at any time without giving reason for doing so and without penalty or prejudice. The investigator is also free to terminate a subject's involvement in the study at any time if the subject's clinical condition warrants it.

If a subject is discontinued from the study with an ongoing adverse event or an unresolved laboratory result that is significantly outside of the reference range, the investigator will attempt to provide follow-up until the condition stabilizes or no longer is clinically significant.

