6.1.1 Study and Treatment Discontinuation

Study and Treatment Discontinuation:

Subjects will be withdrawn from investigational study treatment and all follow-up assessments and will only be followed for mortality through public records if the following occurs:

- Withdrawal of consent by the subject.

Treatment Only Discontinuation:

Subjects will be withdrawn from investigational study treatment if any of the following occur, however, they should continue to be followed according to the protocol Schedule of Assessments (Table 1) and Long Term Follow-up Schedule of Assessments, except post-dose Day 14 safety and laboratory and reactogenicity assessments/visits for those doses not given.

- Investigator's decision that further treatment is not in the best interest of the subject.
- Graft failure.
- Pregnancy (female subjects only).
- Local reactogenicity with a grade ≥ 3 based on the criteria defined in Appendix 4 and is confirmed by a health care professional and reported as a Drug Related Adverse Event.
- Systemic reactogenicity, for any grade ≥ 3 fever or any grade 4 systemic reaction within one week of vaccination and is confirmed by a health care professional and reported as a Drug Related Adverse Event (Appendix 5).
- Anaphylaxis Grade ≥ 3 per NCI ver. 4.03 criteria.

Subjects who discontinue investigational treatment for these or for other reason(s) but do not withdraw consent should remain in the study and continue to be followed according to the visit schedule through the Long-term Follow-up Period. All study procedures should be completed for these subjects, with the exception of the post-dose Day 14 safety laboratory and reactogenicity assessments/visits for those doses that are not given. Subjects not willing to participate in the study procedures should be asked if they would be willing to be followed annually for mortality through the Long-term Follow-up Period.

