In the absence of an explanation for increased LFT's, such as viral hepatitis, pre-existing or acute liver disease or exposure to other agents associated with liver injury, the subject may be discontinued from the study. The investigator may determine that it is not in the subject's best interest to continue study enrollment. Discontinuation of treatment should be considered if:

ALT or AST > 8 × ULN

ALT or AST > 5 × ULN for more than 2 weeks

ALT or AST > 3 × ULN and TBL > 2 × ULN or INR > 1.5) (If INR testing is applicable/evaluated)

ALT or AST $> 3 \times$ ULN with the appearance of fatigue, nausea, vomiting, right upper quadrant pain or tenderness, fever, rash and/or eosinophilia ($> 5\%$).

In addition, if close monitoring for a subject with moderate or severe hepatic laboratory tests is not possible, drug should be discontinued.

*Hy's Law Definition-Drug-induced jaundice caused by hepatocellular injury, without a significant obstructive component, has a high rate of bad outcomes, from 10–50% mortality (or transplant). The two “requirements” for Hy's Law are: 1) Evidence that a drug can cause hepatocellular-type injury, generally shown by an increase in transaminase elevations higher 3 times the upper limit of normal (“2 x ULN elevations are too common in treated and untreated patients to be discriminating”). 2) Cases of increased bilirubin (at least 2 x ULN) with concurrent transaminase elevations at least 3x ULN and no evidence of intra- or extra-hepatic bilirubin obstruction (elevated alkaline phosphatase) or Gilbert's syndrome. [Temple R. Hy's law: predicting serious hepatotoxicity. *Pharmacoepidemiol Drug Saf* 2006 Apr;15(4):241-3.]

Reference

Guidance for Industry titled “Drug-Induced Liver Injury: Premarketing Clinical Evaluation” issued by FDA on July 2009.

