7.4 Analysis of Efficacy

7.4.1 Analysis of Primary Endpoint

7.4.1.1 Primary Analysis of Primary Efficacy Endpoint

The primary efficacy endpoint is the proportion of subjects with CMV viremia which is defined as plasma viral load ≥ 1000 IU/mL assessed by central assay through one year post first Study Drug injection. CMV viral load tests are scheduled once every 2 weeks for the first 8 tests starting 100 days from transplant and subsequently once per month for 7 more tests. In addition, a subject may have unscheduled tests (suspect CMV syndrome or CMV tissue-invasive disease) by the local laboratory so that the subject can be treated promptly with antiviral therapy (AVT) if needed. Everytime a local laboratory is performed, the sample should also be sent to the central laboratory for assessment. The CMV viral load collected from the central laboratory after first injection (Day 1) through day 380 ($=365+14+1$) that were collected as scheduled or unscheduled assessments will be utilized.

A patient who discontinue the study without a positive CMV viral load will be imputed as having a CMV viremia. A patient who has more than one time with viral load ≥ 1000 IU/mL by central assay will be counted once in this summary. Any unscheduled central laboratory values within the window will be included.

A Cochran-Mantel-Haenszel (CMH) test at the 1-sided 5% level stratified by use of anti-thymocyte globulin (ATG) and by receipt of a kidney from a living or deceased donor will be used to analyze the primary endpoint of CMV incidence rate.

The null and alternative hypotheses for this comparison are:

H0: Common Odds Ratio = 1.

H1: Common Odds Ratio < 1.

The odds ratio is defined as the ratio of odds of viremia in the ASP0113 group to that in the placebo group. The 1-sided p-value with the 2-sided exact 90% confidence interval for the

common odds ratio will be calculated (in SAS specifying the comor option in the exact statement of proc freq).

The primary analysis will be conducted for the FAS population.

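### Protocol Section 6.1 and Appendix 10 let an investigator take a subject off the study, Section 6.1.1 keeps that subject in follow-up, and the imputation rules do not agree on how such a subject counts for the primary endpoint.

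*Protocol*

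**What the plan says.** **Routes out of the study.** Under its Study Discontinuation heading, Protocol Appendix 10 says that when a liver-test rise has no explanation "the subject may be discontinued from the study". It adds: "The investigator may determine that it is not in the subject's best interest to continue study enrollment". Stopping treatment comes in a separate sentence with its own numeric criteria. Section 6.1 is broader: "The investigator is also free to terminate a subject's involvement in the study at any time if the subject's clinical condition warrants it".

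**Routes that keep the subject in.** Section 6.1.1 has two lists. In the first, treatment and all follow-up end, and subjects "will only be followed for mortality through public records if the following occurs". Withdrawal of consent is its only entry. The second list is treatment-only discontinuation and includes the investigator's judgement that further treatment is not in the subject's interest. A general rule follows: "Subjects who discontinue investigational treatment for these or for other reason(s) but do not withdraw consent should remain in the study". Neither list mentions Appendix 10 or liver tests.

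**Analysis.** SAP 7.4.1.1 states: "A patient who discontinue the study without a positive CMV viral load will be imputed as having a CMV viremia". Protocol 7.9 and SAP 7.9.1 impute viremia only for subjects lost to follow-up and otherwise not at all. SAP 5.1 excludes from the FAS any subject with no central viral load after the first injection.

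**The concern.** The protocol gives two answers to one question: does a subject whom the investigator takes off for liver tests stay on the viral-load schedule? Footnote 23 to the schedule of assessments gives the mechanics of leaving: a completion visit within 14 days and nothing after it. A site working from Appendix 10 can take that route. A site working from 6.1.1 stops injections and keeps sampling. Both are compliant.

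At stake is how the primary outcome is obtained. The same subject may have an observed outcome at one site and an imputed or missing one at another, because of a decision that began as a safety judgement about injections. These subjects also matter for the endpoint: under Protocol Appendix 7, raised transaminases are one of the findings that, with evidence of CMV in blood, define CMV syndrome, and raised hepatic enzymes enter the definition of CMV hepatitis. Continued viral-load data are therefore informative in them.

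**Working it through.** **1. The protocol passages side by side**

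| Place | Who decides, and why | What ends |
|---|---|---|
| Section 6.1 | Investigator, clinical condition | Involvement in the study |
| Appendix 10 | Investigator, unexplained liver-test rise | Study participation; treatment is dealt with separately |
| Section 6.1.1, first list | Subject withdraws consent | Treatment and all follow-up except mortality from public records |
| Section 6.1.1, second list and general rule | Investigator's decision or other reasons | Treatment only |

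The first two rows cannot be squared with the last for a subject who has not withdrawn consent.

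**2. What happens to a removed subject in the primary analysis**

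- Already at or above 1000 IU/mL on a central sample: an observed event, so removal changes nothing.
- At least one post-dose central sample, none positive: viremic under SAP 7.4.1.1. Under Protocol 7.9 and SAP 7.9.1 this holds only if an investigator's removal counts as loss to follow-up, which neither section defines.
- No post-dose central sample: outside the FAS, hence dropped. This is possible because routine central sampling starts at Day 100 after transplant, while the first three doses fall at Days 30, 60 and 90. A for-cause sample, or one at the completion visit, would bring the subject back in.

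**3. The plan's own sample size**

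Inputs from Protocol 7.1: 46% versus 25%, one-sided 5%, 80% power. The mean rate is 0.355.

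n = [1.645·√(2·0.355·0.645) + 0.842·√(0.46·0.54 + 0.25·0.75)]² / 0.21² = (1.113 + 0.556)² / 0.0441 ≈ 63.2, so 64 per arm.

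The stated 64 is reproduced (power 80.5%). With 70 per arm and no imputation, power is 83.5%. The point does not touch the sample-size arithmetic.

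**4. Size per subject**

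One imputed event in a subject who would otherwise have been non-viremic adds 1/70 = 1.4 percentage points to that arm's rate.

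**5. Illustrative range**

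The documents give no removal rate. Assume k removed subjects per affected arm of 70, all in the FAS, all imputed, and with the arm's usual viremia risk. The rate becomes p′ = p + (k/70)(1 − p). The upper end, k = 6, is the whole loss allowance per arm (70 − 64).

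For k = 3:
- ASP0113: 0.25 + (3/70)(0.75) = 0.282.
- Placebo: 0.46 + (3/70)(0.54) = 0.483.

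| k | Both arms: difference, power | ASP0113 only: difference, power | Placebo only: difference |
|---|---|---|---|
| 0 | 21.0 points, 83.5% | 21.0 points, 83.5% | 21.0 points |
| 1 | 20.7 points, 82.2% | 19.9 points, 79.6% | 21.8 points |
| 3 | 20.1 points, 79.4% | 17.8 points, 70.6% | 23.3 points |
| 6 | 19.2 points, 75.1% | 14.6 points, 55.0% | 25.6 points |

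The sign of the distortion depends on which arm loses more subjects.

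**The case against.** The best reply is that the protocol already resolves the conflict. Section 6.1 defines a discontinuation as the permanent stopping of study treatment, Appendix 10 is only permissive, and the 6.1.1 items on the investigator's decision and other reasons are wide enough to cover liver stops. The last part stands: the absence of liver criteria from the 6.1.1 list is not itself a gap. The rest does not. After that definition, Section 6.1 goes on to say that the investigator is "free to terminate a subject's involvement in the study at any time", and Appendix 10 treats study and treatment separately.

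A reader might also infer four stronger things that the documents do not support:

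- *That a subject removed for liver tests is always counted as viremic.* Only SAP 7.4.1.1 says so. Protocol 7.9 and SAP 7.9.1 are narrower, and the FAS rule may drop the subject.
- *That the primary comparison is biased against the vaccine.* The protocol's safety summary (Section 1.2) names no hepatic signal. Unequal removal is conjecture, and some of these subjects may already be observed viremia events.
- *That the hepatic signal goes unfollowed.* Section 5.5.7 follows adverse events after discontinuation, Section 6.1 asks the investigator to attempt follow-up of unresolved laboratory results, and Appendix 10 sets repeat liver testing. What ends is the scheduled viral-load, graft and general adverse-event collection.
- *That consent withdrawal is the only way off the full schedule.* Section 6.1.1 also offers mortality-only follow-up to subjects unwilling to undergo procedures.

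The Kaplan-Meier sensitivity analysis in SAP 7.4.1.2 censors early leavers at their last assessment. That shows how far the result depends on the imputation but does not recover the missing samples.

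**Conclusion.** The point holds as an inconsistency in current text with a possible, unquantified effect on the primary endpoint. Sections 6.1 and 6.1.1 and Appendix 10 allow compliant sites to differ on whether outcome sampling continues, and the protocol and SAP do not settle how the resulting subject is analysed. The firm figure is 1.4 percentage points per imputed subject who would otherwise have been non-viremic, in an arm of 70. The power figures rest on assumed removal counts of 1 to 6, on full imputation and on average viremia risk; they show sensitivity and are not a forecast. The number affected may be small. The case for change is that the ambiguity is avoidable and bears on the endpoint.

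**What to change.** - Reconcile Protocol Sections 6.1 and 6.1.1 and Appendix 10, with cross-references between Appendix 10 and 6.1.1, so that stopping injections and stopping outcome data collection are separate decisions. Apply consistently the intent that 6.1.1 already states, namely that subjects who stop treatment "but do not withdraw consent should remain in the study and continue to be followed according to the visit schedule". That covers scheduled viral-load, adverse-event, graft and survival follow-up unless consent is withdrawn.
- Align SAP 7.4.1.1, SAP 7.9.1 and Protocol 7.9 so that it is explicit whether a subject removed by the investigator is imputed.

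The cost is a few lines in a protocol amendment, a matching SAP edit and a site memo. The visits concerned are already in the schedule. No view is taken on the liver thresholds or on when treatment should stop.

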12.11 Appendix 11: Common Serious Adverse Events

The following is a list of serious adverse events that the Sponsor considers to be associated with the disease state being studied. **The list does NOT change your reporting obligations or prevent the need to report an adverse event meeting the definition of an SAE as detailed in Section 5.5.3 Definition of Serious Adverse Event (SAE).** The purpose of this list is to alert you that some events reported as SAEs may not require expedited reporting to the regulatory authorities based on the classification of “common serious adverse events”. You are required to follow the requirements detailed in Section 5.5.6 Reporting of Serious Adverse Events (SAE).

For IND safety reporting, single occurrences of the following events may be excluded from expedited reporting to the FDA. If aggregate analysis of these events indicates that they occur more frequently with Study Drug, an expedited IND safety report may be submitted to the FDA.

- Kidney transplant rejection
- Kidney allograft loss
- Blood creatinine increased
- Diabetes mellitus
- Hyperglycemia
- Increase blood glucose

12.12 Appendix 12: Categories of Post Transplant Lymphoproliferative Disorder (PTLD)

Categories of PTLD are the following:

- Early Lesions
 - Reactive plasmacytic hyperplasia
 - Infectious mononucleosis-like
- Polymorphic PTLD
- Monomorphic PTLD (classify according to lymphoma classifications)
 - B cell neoplasms
 - Diffuse large B cell lymphoma (immunoblastic, centroblastic, anaplastic)
 - Burkitt/Burkitt-like lymphoma
 - Plasma cell myeloma
 - Plasmacytoma-like lesions
 - Maltoma
 - T cell neoplasm
 - Peripheral T cell lymphoma, unspecified type
 - Anaplastic large cell lymphoma (T or null cell)
 - Hepatosplenic gamma-delta T cell lymphoma
 - Other (i.e., T-NK type)
- Hodgkin lymphoma and Hodgkin lymphoma-like PTLD

Reference:

AJT Infectious Disease Community. Epstein-Barr virus and lymphoproliferative disorders after transplantation. *Am J Transplantation* 2004; 4(Suppl. 10): 59-65.

12.13 Appendix 13: EQ-5D Questionnaire

Note that the below is an example; subjects will be provided with forms to be completed.

Under each heading, please tick the ONE box that best describes your health TODAY

MOBILITY

- I have no problems in walking about
- I have slight problems in walking about
- I have moderate problems in walking about
- I have severe problems in walking about
- I am unable to walk about

SELF-CARE

- I have no problems washing or dressing myself
- I have slight problems washing or dressing myself
- I have moderate problems washing or dressing myself
- I have severe problems washing or dressing myself
- I am unable to wash or dress myself

USUAL ACTIVITIES (e.g. work, study, housework, family or leisure activities)

- I have no problems doing my usual activities
- I have slight problems doing my usual activities
- I have moderate problems doing my usual activities
- I have severe problems doing my usual activities
- I am unable to do my usual activities

PAIN / DISCOMFORT

- I have no pain or discomfort
- I have slight pain or discomfort
- I have moderate pain or discomfort
- I have severe pain or discomfort
- I have extreme pain or discomfort

ANXIETY / DEPRESSION

- I am not anxious or depressed
- I am slightly anxious or depressed
- I am moderately anxious or depressed
- I am severely anxious or depressed
- I am extremely anxious or depressed

[figure not shown]
UK (English) v.2 © 2009 EuroQol Group. EQ-5D™ is a trade mark of the EuroQol Group

Appendix 13: EQ-5D Questionnaire continued

- We would like to know how good or bad your health is TODAY.
- This scale is numbered from 0 to 100.
- 100 means the best health you can imagine.
0 means the worst health you can imagine.
- Mark an X on the scale to indicate how your health is TODAY.
- Now, please write the number you marked on the scale in the box below.

YOUR HEALTH TODAY =

The best health
you can imagine

[figure not shown]

The worst health
you can imagine

- We would like to know how good or bad your health is TODAY.
- This scale is numbered from 0 to 100.
- 100 means the best health you can imagine.
0 means the worst health you can imagine.
- Mark an X on the scale to indicate how your health is TODAY.
- Now, please write the number you marked on the scale in the box below.

YOUR HEALTH TODAY =

The best health
you can imagine

[figure not shown]
The worst health
you can imagine

UK (English) v.2 © 2009 EuroQol Group. EQ-5D™ is a trade mark of the EuroQol Group

- We would like to know how good or bad your health is TODAY.
- This scale is numbered from 0 to 100.
- 100 means the best health you can imagine.
0 means the worst health you can imagine.
- Mark an X on the scale to indicate how your health is TODAY.
- Now, please write the number you marked on the scale in the box below.

YOUR HEALTH TODAY =

The best health
you can imagine

The worst health
you can imagine

UK (English) v.2 © 2009 EuroQol Group. EQ-5D™ is a trade mark of the EuroQol Group

12.14 Appendix 14: Kidney Transplant Questionnaire (KTQ-34)

INSTRUCTION: This questionnaire asks for your views about your health-related quality of life. Please read each question very carefully and mark the response that best reflects your experience. Please note that the different sections ask for different types of responses. Please choose only one answer for each item and do not skip any items.

Amount of Time In the Past Two Weeks							
	All of the time	Most of the time	A Good Bit of the time	Some of the time	A little of the time	Hardly Any of the time	None of the time
1. How often in the past two weeks have you felt weak?	1	2	3	4	5	6	7
2. How often in the past two weeks have you felt impatient?	1	2	3	4	5	6	7
3. How often in the past two weeks have you felt depressed?	1	2	3	4	5	6	7
4. How often in the past two weeks have you felt stubborn?	1	2	3	4	5	6	7
5. How often in the past two weeks have you felt sluggish?	1	2	3	4	5	6	7
6. How often in the past two weeks have you felt anxious?	1	2	3	4	5	6	7
7. How often in the past two weeks have you felt fear or panic related to graft rejection?	1	2	3	4	5	6	7
8. How often in the past two weeks have you felt uncertain about your future?	1	2	3	4	5	6	7
9. How often in the past two weeks have you felt worried?	1	2	3	4	5	6	7
10. How often in the past two weeks have you felt protective of your transplant?	1	2	3	4	5	6	7
11. How often in the past two weeks have you felt irritable, difficult to get along with?	1	2	3	4	5	6	7
12. How often in the past two weeks have you felt generally frustrated?	1	2	3	4	5	6	7
13. How often in the past two weeks have you felt low in energy?	1	2	3	4	5	6	7
14. How often in the past two weeks have you felt dizzy or lightheaded?	1	2	3	4	5	6	7

Appendix 14: Kidney Transplant Questionnaire (KTQ-34) continued:

	Amount of Trouble or Distress						
	A Very Great Deal	A Great Deal	A Good Deal	A moderate Amount	Some	Very Little	None
15. In the past two weeks, how much trouble or distress have you had because of excessive appetite?	1	2	3	4	5	6	7
16. In the past two weeks, how much trouble or distress have you had because of excessive hair growth?	1	2	3	4	5	6	7
17. In the past two weeks, how much trouble or distress have you had because of very little strength?	1	2	3	4	5	6	7
18. In the past two weeks, how much trouble or distress have you had because of increased tiredness?	1	2	3	4	5	6	7
19. In the past two weeks, how much trouble or distress have you had because of excessive weight?	1	2	3	4	5	6	7
20. In the past two weeks, how much trouble or distress have you had because of acne?	1	2	3	4	5	6	7
21. In the past two weeks, how much trouble or distress have you had because of difficulty sleeping?	1	2	3	4	5	6	7
22. In the past two weeks, how much trouble or distress have you had because of trembling in your body, hands or fingers?	1	2	3	4	5	6	7
23. In the past two weeks, how much trouble or distress have you had because of ache or pain in your joints?	1	2	3	4	5	6	7
24. In the past two weeks, how much trouble or distress have you had because of ache or pain in your feet and legs?	1	2	3	4	5	6	7
25. In the past two weeks, how much trouble or distress have you had because of ache or pain in your shoulder and arms?	1	2	3	4	5	6	7
26. In the past two weeks, how much trouble or distress have you had because of muscle cramps?	1	2	3	4	5	6	7

Appendix 14: Kidney Transplant Questionnaire (KTQ-34) continued:

	Amount of Trouble or Distress						
	A Very Great Deal	A Great Deal	A Good Deal	A moderate Amount	Some	Very Little	None
27. In the past two weeks, how much trouble or distress have you had because of not seeing clearly?	1	2	3	4	5	6	7
28. In the past two weeks, how much trouble or distress have you had because of swollen or bleeding gums?	1	2	3	4	5	6	7
29. In the past two weeks, how much trouble or distress have you had because of swelling in your ankles or legs?	1	2	3	4	5	6	7
30. In the past two weeks, how much trouble or distress have you had because of abdominal bloating?	1	2	3	4	5	6	7
31. In the past two weeks, how much trouble or distress have you had because of shortness of breath?	1	2	3	4	5	6	7
32. In the past two weeks, how much trouble or distress have you had because of headaches?	1	2	3	4	5	6	7
33. In the past two weeks, how much trouble or distress have you had because of your medication dosing schedule or the number of pills you take?	1	2	3	4	5	6	7
34. In the past two weeks, how much trouble or distress have you had because of decreased sexual interest or sexual activities?	1	2	3	4	5	6	7

